1.0 OBJECTIVES

1.1 Primary Objectives

1.1.1 Phase I: To determine the DLT and MTD of the combination of quizartinib (AC220) with either 5-azacitidine (AZA) or low-dose cytarabine (LDAC) in patients with acute myeloid leukemia (AML) or high-risk myelodysplastic syndrome (MDS).

1.1.2 Phase II: To determine the clinical activity of the combination of quizartinib with either AZA or LDAC in patients with AML or MDS.

1.2 Secondary Objectives:

1.2.1 Phase I: To determine the clinical activity of the combination of quizartinib with either AZA or LDAC in patients with AML or MDS.

1.2.2 Phase II: To determine the safety of the combination of quizartinib with either AZA or LDAC in patients with AML or MDS.

1.2.3 Both:

1.2.3.1 To determine the induction of hypomethylation, DNA damage and FLT3 signaling during therapy with this combination and its correlation with response.

1.2.3.2 To determine the effect of this combination therapy on plasma levels of FLT3-ligand

1.2.3.3 To determine the pharmacodynamics of this combination therapy in patients with AML or high-risk MDS.

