- 2.4 Recently, the results of a randomized trial comparing two lower doses of quizartinib were reported. In this trial, patients with relapsed or refractory AML with FLT3 mutation were randomized to receive quizartinib 30 mg or 60 mg orally, daily. A total of 76 patients were enrolled (38 to each arm). The overall composite response rate (CRc, which was the primary endpoint) was identical for the two arms (47%). The overall response rate was slightly higher with 60 mg daily (71%) than with 30 mg daily (61%) because of a higher rate of partial responses in the 60mg arm (24%) compared to the 30 mg arm (13%). QTc prolongation to >500 msec (the dose limit⁹⁸ toxicity for quizartinib) occurred in only 3% with 60 mg and 5% with 30 mg. When comparing these results with a prior study exploring higher doses (90 mg, 135 mg, and 200 mg) it is clear that the rate of CRc is identical at all dose levels with some increase in PR with progressively higher doses. However, QTc prolongation is clearly dose dependent and prolongations >60 msec from baseline occur in 40% or more of the patients treated at doses of 90mg or above, exceeding the threshold of acceptable grade 3 toxicity for the standard definition of MTD. Although these prolongations have been asymptomatic and transient, resolving with lower doses, based on this new data we have decided not to explore a dose level of 90 mg daily and expand 60

mg (i.e., the starting dose level) for the phase 2 portion of the study provided MTD is not exceeded as defined in the protocol section 5.2.5. If MTD is exceeded at this dose level, 30 mg will be explored.

	2689-CL-2004		AC220-002 (Cohort 2)		
	30 mg/day (N = 38)	60 mg/day (N = 38)	90 mg/day (N=57)	135 mg/day (N=67)	200 mg/day (N=12)
Best Response					
CRc Rate	47%	47%	47%	45%	42%
PR Rate	13%	24%	25%	28%	50%
Maximum change in QTcF from baseline (msec)					
≤ 30	50%	44%	9%	9%	0%
> 30 to ≤ 60	47%	36%	46%	51%	8%
> 60	3%	19%	46%	39%	92%

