5.0 TREATMENT PLAN

5.1 General

All patients will be registered through CORE. The objective will be to administer AZA or LDAC, and quizartinib at dose level 0 as defined in the Table below. We will first treat 6 patients at dose level -1. If no DLT is identified in >1 patient, this level is defined as MTD and up to 20 patients will be treated at this level with each treatment combination (AC220+ AZA or AC220 + LDAC) for the phase II portion. Other dose levels will be used for dose adjustments for toxicity during therapy.

Approximately 200 patients will be enrolled on this study.

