- 5.2.5** DLT is defined as any clinically significant non-hematologic adverse event or abnormal laboratory value occurring during the first cycle on study unless the event or laboratory value can clearly be determined to be unrelated to AC220 with the following exceptions:
- CTCAE Grade 3 or 4 AST (SGOT) or ALT (SGPT) that resolves to \leq grade 2 in 14 days
 - Grade 3 nausea, vomiting, or diarrhea that can be managed to \leq grade 2 with standard antiemetic or antidiarrheal medications used at prescribed dose within 7 days of onset.
 - Grade 4 vomiting, or diarrhea that can be managed to \leq grade 3 with standard antiemetic or antidiarrheal medications used at prescribed dose within 48 hours of onset.
 - Grade 3 or 4 electrolyte abnormalities will only be considered DLT if possibly related to study drug and not corrected by optimal replacement therapy within 48 hours.
 - Grade 3 biochemical abnormalities of amylase or lipase without evidence of clinical pancreatitis.
 - Grade 3 anorexia or fatigue.
 - Grade 3 or 4 QTc prolongation will constitute DLT as follows: The QTc interval will be calculated by Fridericia's correction factor (QTcF). If the QTc is > 500 msec the EKG must be evaluated within 2 hours in triplicate and if \geq grade 3 QTc prolongation is confirmed this will be considered a DLT.

Hematologic DLT is defined as grade ≥ 3 neutropenia and/or thrombocytopenia with a hypocellular bone marrow lasting for 6 weeks or more after the start of a course in the absence of residual leukemia (i.e., with less than 5% blasts). Anemia will not be considered for the definition of DLT.

- 5.2.5.1** If DLT occurs in $\geq 2/6$ patients, this dose level would exceed the MTD, and an additional 6 patients will be treated at the next lower dose level. The dose level at which 0-1/6 patients experience DLT (but not higher than 60 mg/day) will be used to treat a maximum of 20 patients in each cohort in the phase II portion of the study. If $\geq 2/6$ patients experience DLT at dose level -1 in any arm, dose level -2 may be explored for that arm(s).
- 5.2.5.2** If DLT is observed in 0 or 1/6 in dose level 1, this cohort will be expanded to treat up to 20 patients in the phase II portion of the study. If $\geq 2/6$ patients experience DLT at dose level 1 for any arm of the study, the dose level at which $\leq 1/6$ patients have experienced DLT will be used for the phase II portion of the study for that arm.

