12.2 Phase I

The primary objective of the phase I portion of the study is to determine the MTD of each combination therapy. The dose schedule is listed in table 1 of section 5.2.1. Up to 2 dose levels of AC220 will be tested in each combination with a fixed dose of the other drug. Initially, 6 patients will be treated at dose level1, if ≤ 1 patients experience DLT at dose level1, then 6 subsequent patients will be treated at the next higher dose level, dose level2. If ≤ 1 patients experience DLTs in dose level2, this level will be defined as the MTD and will be used in the phase II portion of the study. If > 1 patients experience DLTs at dose level1, then the 6 subsequent patients will be treated at the next lower dose level, level -1. The MTD is defined as the highest dose at which no more than 1 patient experiences DLTs. For each combination therapy, 12 patients will be evaluated. The total sample size for the phase I portion will be 24.

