Where P_E and P_S denote the response rate for experimental and standard treatment, respectively, and θ_E denotes the toxicity rate for the experimental treatment combination. Assume $P_E \sim$ prior beta(0.6, 1.4) and $\theta_E \sim$ prior beta(0.6, 1.4).

That is, the trial in this cohort will be stopped early for futility if the data indicate that there is more than 98% probability that the response rate is not improved by 15% or the trial will be stopped early for toxicity if the data indicate that there is more than 90% probability that the toxicity rate (i.e. DLT rate) is more than 30%. The corresponding stopping boundaries for futility is: the trial in this cohort will be stopped early if (the number of response observed / among number of patients) in this cohort $\leq 3/15, 4/20, 6/25, 8/30, 10/35, 11/40$ and $13/45$.

The corresponding stopping boundaries for toxicity is: The trial will be stopped early in this cohort if (the number of patients experienced DLTs / among number of patients) in this cohort $\geq 8/15, 9/20, 11/25, 13/30, 15/35, 16/40$ and $18/45$.

Table 3 presents the operating characteristics for the above design.

Table 3: OCs for the design for cohort 2B

Response rate	Toxicity rate	Probability of early stopping	Average number of patients
0.3	0.1	0.64	33
0.3	0.3	0.72	30.6
0.3	0.5	0.99	18.8
0.45	0.1	0.08	47.8
0.45	0.3	0.27	43
0.45	0.5	0.96	20.9
0.6	0.1	0.002	49.9
0.6	0.3	0.21	44.8
0.6	0.5	0.96	21.2

If the trial in one group continues until 50 patients are evaluated, and assuming the overall response rate is 45%, then the 95% credible interval for overall response rate would be (0.31, 0.58).

12.4 Analysis Plan:

For discrete or categorical data, descriptive statistics will include tabulations of frequencies. For continuous data, summary statistics including n, mean, standard deviation, median, minimum and maximum will be computed. The posterior response rate and its 95% credible intervals will be estimated.

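### On some of its phase I dose paths the plan can name a level the MTD, or stop looking for one, after 0-1/6 DLTs with no higher level tested, so a pass shows tolerability in six patients and not an upper limit

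*Combined protocol and SAP*

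**What the plan says.** The phase I primary objective (1.1.1) is "To determine the DLT and MTD of the combination of quizartinib (AC220) with either 5-azacitidine (AZA) or low-dose cytarabine (LDAC"), and 12.2 repeats it: "The primary objective of the phase I portion of the study is to determine the MTD of each combination therapy". The sections then describe different paths to that result.

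- **Section 5.1** treats six patients at level -1 and states: "If no DLT is identified in >1 patient, this level is defined as MTD".
- **Section 12.2** starts at level 1: "Initially, 6 patients will be treated at dose level1, if ≤ 1 patients experience DLT at dose level1, then 6 subsequent patients" go to level 2. Level 2 becomes the MTD if at most one of its six patients has a DLT. If level 1 has more than one DLT, six patients are treated at level -1. The general definition is "The MTD is defined as the highest dose at which no more than 1 patient experiences DLTs".
- **Sections 2.4 and 5.2.5** remove level 2 from testing. Section 2.4 says "we have decided not to explore a dose level of 90 mg daily". Section 5.2.5.2 says "If DLT is observed in 0 or 1/6 in dose level 1, this cohort will be expanded to treat up to 20 patients", and 5.2.5.1 caps the phase II dose at 60 mg/day. These sections choose a phase II dose and do not themselves call it the MTD.

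Section 12.3 counts six phase I patients treated at the MTD within the 26 for the low-dose cytarabine regimen, so the label carries into phase II. Section 12.3 also monitors DLTs in every phase II group under a beta(0.6, 1.4) prior. For estimation, 12.4 says "The posterior response rate and its 95% credible intervals will be estimated" and names no such summary for the DLT rate.

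**The concern.** An MTD is a statement about an upper limit: this level is tolerated and the next one is not. To support it, the trial needs a failing result at the next higher level. Where a level is called the MTD after 0-1/6 and nothing above it was tried, the data support only the first half of that statement. If few DLTs occur, the primary phase I conclusion would then claim a limit that the design did not look for.

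Six patients also say little in the other direction, because 0-1/6 is compatible with DLT rates above the plan's own 30% limit. Phase II will add many more patients at the same dose, but 12.4 does not ask for their DLT data to be summarised as an estimate with an interval.

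**Working it through.** **Inputs.** Six patients per level, with a pass defined as 0 or 1 DLT (5.1, 5.2.5, 12.2). Dose levels as in Tables 1(a) and 1(b) of 5.2.1; level 2 is the highest. Toxicity prior beta(0.6, 1.4) and limit 0.30 (12.3.2). The documents give no DLT rate for either combination, so the rates below are assumptions. The only nearby figure is in 2.4: QTc above 500 msec in 3% of patients at 60 mg and 5% at 30 mg with quizartinib alone.

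**The plan's own figure.** Six patients × 2 levels × 2 combinations = 24, as 12.2 states. This needs two levels in each arm. Under 2.4 and 5.2.5, a pass at level 1 uses six patients per arm, or 12 in total.

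**Which MTD calls rest on a failed higher level.**

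| Section | Level selected | Higher level tested and failed? |
|---|---|---|
| 5.1 | -1, after 0-1/6 | No, none tested |
| 12.2 | 2, after 0-1/6 at levels 1 and 2 | No, none exists |
| 12.2 | 1 | Yes, level 2 failed |
| 12.2 | -1 | Yes, level 1 failed |
| 2.4 and 5.2.5 | 1, expanded after 0-1/6 | No, none assigned |
| 5.2.5 | -1, after level 1 failed | Yes, level 1 failed |

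**Chance that a level passes.** P(pass) = (1−p)^6 + 6p(1−p)^5. At p = 0.10 this is 0.531 + 0.354 = 0.886.

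| True DLT rate | P(0-1/6) |
|---|---|
| 3% | 0.988 |
| 5% | 0.967 |
| 10% | 0.886 |
| 15% | 0.776 |
| 20% | 0.655 |
| 30% | 0.420 |
| 40% | 0.233 |

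**The 12.2 path.** With independent levels, P(level 2 named MTD with no level failed) = P(pass level 1) × P(pass level 2). P(MTD bracketed by a failed higher level) = P(pass level 1) × P(fail level 2) + P(fail level 1) × P(pass level -1).

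| Assumed rates at levels -1, 1, 2 | Level 2 named, none failed | Bracketed MTD |
|---|---|---|
| 5%, 5%, 5% | 0.936 | 0.063 |
| 10%, 10%, 10% | 0.785 | 0.202 |
| 5%, 10%, 15% | 0.688 | 0.308 |
| 10%, 20%, 30% | 0.275 | 0.685 |

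The first two rows assume a flat dose-toxicity curve and the last two a rising one. Under 5.1 after a pass at level -1, or under 2.4 and 5.2.5 after a pass at level 1, the chance of a bracketed MTD is 0 by construction.

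**What six patients say about the DLT rate.** After 1/6 the posterior is beta(0.6 + 1, 1.4 + 5) = beta(1.6, 6.4). Its 95% interval is 0.02 to 0.52, and Pr(θ_E > 0.30) = 0.21. For comparison, 15 DLTs in 50 patients give beta(15.6, 36.4), with an interval of 0.18 to 0.43.

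**What stopping rules alone leave unreported.** In the low-dose cytarabine regimen, 10 DLTs in 26 patients need not cross a listed toxicity boundary if the tenth comes late enough (10/24 is below 11/24). The posterior is then beta(10.6, 17.4), with a 95% interval of 0.21 to 0.56 and Pr(θ_E > 0.30) = 0.80. Section 12.4 does not require this to be shown beside an MTD based on six patients.

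**The case against.** The strongest reply is that 12.2 is largely a proper search. Passing level 1 is not an MTD call there; it leads to level 2. Level 1 is the MTD only if level 2 fails, and level -1 is reached only after level 1 fails. That is correct. A reader might infer from the one-sentence definition in 12.2 that any level becomes the MTD on its own six patients, but the steps in that section do not support this for levels 1 and -1.

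Second, 2.4 and 5.2.5 do not call level 1 the MTD. They choose a capped phase II dose and give a reason: similar composite response rates across doses, and QTc prolongation that rises with dose. This also stands, and the decision to stop escalating is not in question. But those data are for quizartinib alone and concern changes above 60 msec, whereas the QTc DLT in 5.2.5 is a confirmed value above 500 msec and 5.2.5.5 defines the MTD separately for each combination. They explain the cap without measuring the MTD named in 1.1.1.

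Third, a reader might infer that the MTD call is close to automatic. That describes only true DLT rates of about 5% or less. The 3% and 5% figures are single-agent QTc rates, the DLT definition is much broader, and the regimens add a second drug. At 10% the chance is already 0.79 (two levels) to 0.89 (one level). If level 2 had a DLT rate of 46%, borrowing the 90 mg figure for changes above 60 msec in 2.4 purely as an illustration, and level 1 had 10%, level 2 would be named only 0.886 × 0.152 = 0.13 of the time.

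Fourth, too toxic a dose is already guarded against, since 12.3 monitors DLTs on accumulating data, including phase I patients at the same dose. This stands as a safety rule. It does not show that the dose is the maximum tolerated one, and it is a trigger for stopping, not a reported estimate.

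**Conclusion.** The point holds for three outcomes: level -1 under 5.1, level 2 under 12.2, and level 1 under 2.4 and 5.2.5 after a pass. In the first two the plan uses the term MTD without a failed higher level. In the third it does not use the term, but objective 1.1.1 cannot be met. The point does not hold for levels 1 and -1 on the 12.2 path.

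A pass has probability 0.97, 0.89, 0.66 and 0.42 at true DLT rates of 5%, 10%, 20% and 30%. These rates are assumptions, and the two-level figures also assume that levels are independent. What is at stake is what the trial may conclude about its phase I primary objective; patient safety monitoring and the choice of cap are not affected. The change is worth making because it corrects a primary conclusion at almost no cost.

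**What to change.** 1. In 1.1.1, 5.1 and 12.2, report an MTD for an arm only when the next higher level in that arm was tested and had at least 2/6 DLTs. Otherwise report *MTD not reached; recommended phase II dose*.
2. In 12.4, add for each regimen the final posterior DLT rate, its 95% credible interval and Pr(θ_E > 0.30) under the existing beta(0.6, 1.4) prior, using all DLT-evaluable patients treated at that dose in phases I and II.
3. Reconcile 2.4, 5.1, 5.2.1.1, 5.2.3, 5.2.5 and 12.2. They conflict on the starting level (-1 in 5.1; 1 in 5.2.1.1, 5.2.3 and 12.2) and on whether level 2 is tested or used (12.2 against 2.4 and the cap in 5.2.5.1). This review does not say which is right. The phase I total of 24 in 12.2 should then be checked against the path that is kept.

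Items 1 and 2 need wording and one extra summary of data already collected, with no extra patients or procedures. Item 3 is a decision for the sponsor and investigators. The downside is a less definite headline, because the trial may report no MTD.

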12.3 Phase II

A: Cohort 2A – FLT3-ITD

The primary endpoint of the phase II portion of the study is overall response (CR+Cri+PR+HI) (first 2 treatment courses). It would be encouraging if the overall response rate reaches 50%.

Treatment with AC220 + low-dose cytarabine (Cohort 2A-FLT3-ITD)

Patients enrolled in the treatment of AC220 + low-dose cytarabine could be newly diagnosed or previously treated. A total of 26 patients (including 6 patients treated at MTD in Phase I) will be treated with this treatment combination. The toxicity and efficacy (CR+Cri+PR+HI) will be monitored during the study, and all the data will be used to update the prior distributions for toxicity and efficacy parameters. The study will be stopped for toxicity and futility based on the following stopping rules. If the trial for this treatment continues until 26 patients are evaluated, and assuming the overall response rate is 50%, then the 95% credible interval for overall response rate would be (0.32, 0.68).

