- 5.2.5.3** If DLT is observed in 2/6 patients treated at dose level 1 in any arm, the study will continue at the quizartinib dose of 30 mg PO (dose level -1) for that arm to treat an additional 26 patients at this dose level in the phase II portion of the study.
- 5.2.5.4** Patients that are removed from study before day 28 for any reason other than toxicity and have not experienced DLT will be replaced.
- 5.2.5.5** DLT and MTD will be defined independently for each treatment arm (i.e., AC220 + AZA and AC220 + cytarabine).
- 5.2.6** One cycle of therapy is defined 7 days of AZA or 10 days of LDAC, and 28 days of quizartinib. Patients will receive one cycle of therapy every 4 weeks.
 - 5.2.6.1** Cycles may be started early (but not earlier than day 21) for patients with active disease if judged in the best interest of the patient.
 - 5.2.6.2** Subsequent cycles may be delayed for recovery of toxicity. Delays in start of subsequent cycles greater than 8 weeks should be discussed with the principal investigator.

5.2.6.3 Quizartinib therapy may continue if there is a delay in the start of the next cycle of AZA provided the delay is not due to toxicity possibly related to quizartinib.

5.2.6.4 Subsequent courses may be administered regardless of peripheral blood counts during the first 4 cycles and/or in the presence of residual leukemia. If prolonged myelosuppression (more than 60 days) with evidence of a hypocellular marrow (marrow cellularity less than 5% without evidence of leukemia) is observed subsequent courses of AZA may be given at the next lower dose. If the peripheral counts do not recover (ANC $<1 \times 10^9/L$ and/or platelets $<30 \times 10^9/L$) but there is evidence of residual leukemia in the bone marrow, subsequent cycles can be administered at the discretion of the treating physician not earlier than 3 weeks after the prior cycle.

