5.3 Duration of Therapy

In the absence of treatment delays due to adverse events, treatment may continue until one of the following criteria applies:

1. Clinically significant progressive disease
2. Grade 4 QTc prolongation.
3. Intercurrent illness that prevents further administration of treatment

4. Patient request
5. General or specific changes in the patient's condition render the patient unacceptable for further treatment in the judgment of the investigator.
6. Unacceptable toxicity that in the opinion of the investigator makes it unsafe to continue therapy. This includes patients with grade 4 non-hematological toxicity unless it reverses to grade ≤ 1 on or before 14 days of interrupting AC220.

5.3.1 It is planned that up to a total of 12 cycles of therapy will be administered for patients deriving benefit from this regimen. Continuation of therapy for patients completing 12 cycles of therapy may be considered on a case by case basis after discussion with the principal investigator.

5.3.2 A minimum of 1 full course (defined as the administration of AZA for 7 days or LDAC for 10 days, and quizartinib for 24 days for cycle one, i.e. days 5-28) will be required for a patient to be considered as having received an adequate trial to evaluate efficacy. All patients receiving at least one dose of any of the two drugs will be considered evaluable for toxicity.

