12.3.1 Overall response

Response will be monitored closely in patients using the method of Thall et al (1995). Denote the probability of overall response by P_E . We assume $P_E \sim \text{beta}(1, 1)$. We will stop the trial of this treatment if at any point $\text{Pr}(P_E < 0.5 \mid \text{data}) > 0.98$. That is, we will stop the treatment of this combination if, at any time during the study, we determine that there is more than 98% chance that the response rate is less than 50%. The trial will be stopped if (the number of response observed / among number of patients) $\leq 1/10, 2/12, 3/15, 4/18, 5/21, \text{ and } 6/24$.

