12.3.2 Toxicity

Toxicity will be monitored closely using the method of Thall et al (1995). Denote the probability of toxicity by θ_E , where toxicity is defined as DLTs. We assume $\theta_E \sim \text{beta}(0.6, 1.4)$. We will stop the trial if at any point $\Pr(\theta_E > 0.30 \mid \text{data}) > 0.9$. That is, we will stop the trial of this combination therapy if, at any time during the study, we determine that there is more than 90% chance that the toxicity rate is more than 30%. The trial will be stopped if (the number of toxicity observed / among number of patients) $\geq 6/11, 7/14, 8/16, 9/19, 10/22$ and $11/24$.

Table 1 presents operating characteristics for the study design.

Table 1: Operating characteristics

Response rate	Toxicity rate	Probability of early stopping	Average number of patients
0.2	0.1	0.862	15.01
	0.2	0.864	14.94
	0.3	0.884	14.48
	0.4	0.929	13.37
	0.5	0.974	11.95
0.3	0.1	0.497	20.31
	0.2	0.508	20.14
	0.3	0.579	19.11
	0.4	0.743	16.64
	0.5	0.907	13.62
0.4	0.1	0.175	24.02
	0.2	0.192	23.79
	0.3	0.309	23.33
	0.4	0.577	18.88
	0.5	0.847	14.72
0.5	0.1	0.038	25.54
	0.2	0.058	25.29
	0.3	0.194	23.65
	0.4	0.507	19.79
	0.5	0.822	15.16
0.6	0.1	0.005	25.93
	0.2	0.026	25.67
	0.3	0.167	23.99
	0.4	0.49	20.02
	0.5	0.816	15.27

MultcLean V1.2 developed in the Department of Biostatistics MDACC was used to calculate the stopping boundaries for futility and toxicity monitoring rules.

Treatment with AC220 + 5-azacytidine (Cohort 2A-FLT3-ITD)

Up to 50 newly diagnosed patients (including patients treated at the same dose in phase I) and up to 50 previously treated patients (including patients treated at the same dose in phase I) will be treated with AC220 + 5-azacytidine. The analysis for the two groups of patients will be completed separately.

The study will monitor futility and safety for each patient group and the monitoring will begin when 15 patients have been enrolled in that group, and thereafter by a cohort of 5 patients. The trial in one group will be stopped early if at any time point the data in that group suggest

$$\Pr(P_E < 0.5 \mid \text{data}) > 0.98 \text{ or}$$

$$\Pr(\theta_E > 0.30 \mid \text{data}) > 0.9$$

Where P_E denote the response rate for experimental treatment, and θ_E denotes the toxicity rate for the experimental treatment combination. Assume $P_E \sim$ prior beta(1,1) and $\theta_E \sim$ prior beta(0.6, 1.4).

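### The replacement rule, the fixed six-patient LDAC carry-over and the full-course requirement together let treated patients who leave before day 28 drop out of the primary response rate and futility monitoring

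*Combined protocol and SAP*

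**What the plan says.** Section 12.2 sets the phase I cohort size: "Initially, 6 patients will be treated at dose level1". Section 5.2.5.4, among the DLT and MTD rules, adds: "Patients that are removed from study before day 28 for any reason other than toxicity and have not experienced DLT will be replaced". That sentence does not restrict itself to phase I.

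Section 12.3 defines the phase II primary endpoint for Cohort 2A as "overall response (CR+Cri+PR+HI) (first 2 treatment courses"), with a target: "It would be encouraging if the overall response rate reaches 50"%. For LDAC it fixes the number carried over from phase I: "A total of 26 patients (including 6 patients treated at MTD in Phase I) will be treated with this treatment combination". For AZA it gives no number: "Up to 50 newly diagnosed patients (including patients treated at the same dose in phase I"), with parallel wording for previously treated patients.

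Section 5.3.2 defines a minimum of one full course, with quizartinib on days 5 to 28 of cycle 1, which "will be required for a patient to be considered as having received an adequate trial to evaluate efficacy". It names both AZA and LDAC and is not tied to a phase.

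Section 12.4 (Analysis Plan) names no analysis set. Section 12.3 says only that all data update the priors.

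**The concern.** Replacement is a sensible device for a DLT assessment, because a patient who leaves early for another reason says little about first-cycle toxicity. It is not neutral for a response rate. Non-toxicity reasons for stopping in Section 5.3 include progression, intercurrent illness and patient request, and the first on-treatment marrow is due on day 28 with a 7-day window (Section 9.2.4). Most patients who leave before day 28 will therefore have no documented response.

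If one phase I LDAC patient at the MTD is replaced, seven have been treated at that dose, but Section 12.3 admits six. The plan does not say which six. The natural choice is the six who completed DLT evaluation, which omits the patient who left. Section 5.3.2 can produce the same omission by another route in either arm, since a patient removed before day 28 cannot have taken quizartinib through day 28.

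At stake are the primary response estimate, which would be too high, and the futility rule, which would stop less often than it should.

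**Working it through.** **Inputs.** LDAC sample size 26, of whom 6 come from phase I (12.3). Beta(1,1) prior for response; stop if Pr(P_E < 0.5 | data) > 0.98; listed stopping boundaries 1/10, 2/12, 3/15, 4/18, 5/21 and 6/24 (12.3.1). The number of replaced patients, k, is not in the documents. I assume k = 1 to 3, all non-responders.

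**Reproducing the plan's figures.** With x responses in n patients the posterior is Beta(1 + x, 1 + n − x). For 13/26 this is Beta(14, 14), with central 95% interval 0.319 to 0.681, matching the stated (0.32, 0.68). Applying the listed boundaries for futility alone, with exact binomial probabilities and a true response rate of 30%, gives a stopping probability of 0.497, as in Table 1 of 12.3.2 (response 0.3, toxicity 0.1).

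**Effect on the estimate.** Keep 13 responses and add k treated non-responders to the denominator:

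| k | Responses/patients | Rate | 95% credible interval | Change from 50.0% |
|---|---|---|---|---|
| 0 | 13/26 | 50.0% | 0.32 to 0.68 | – |
| 1 | 13/27 | 48.1% | 0.31 to 0.66 | −1.9 points |
| 2 | 13/28 | 46.4% | 0.29 to 0.64 | −3.6 points |
| 3 | 13/29 | 44.8% | 0.28 to 0.63 | −5.2 points |

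**Effect on a futility decision.** The posterior probability that the response rate is below 0.5, without and with the omitted patients:

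- 2/10: 0.967, continue. One omitted patient counted, 2/11: 0.981, stop. Two counted, 2/12: 0.989, stop.
- 4/15: 0.962, continue. One counted, 4/16: 0.976, still continue.
- 7/24: 0.978, continue. One counted, 7/25: 0.986, stop.

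The 2/11 and 7/25 results cross the stated probability threshold, but the listed boundaries have no entry at 11 or 25 patients. The 2/12 result is itself a listed boundary, so with two omitted patients the decision changes under either form of the rule.

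**Effect on the stopping probability.** Use the listed boundaries, futility only. Suppose k early non-responders are counted first among the 26 and the remaining patients respond at 30%. The stopping probability rises from 0.497 to 0.56, 0.63 and 0.70 for k = 1, 2 and 3. Leaving those patients out gives up that increase.

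**The case against.** The strongest objection is that no sentence excludes anyone. Section 12.3 speaks of patients treated, not patients evaluable for DLT; six is simply the planned cohort size; and all data are said to update the priors. This stands to the extent that the defect is an unresolved denominator and not a stated exclusion. It does not remove the problem, because a fixed six cannot hold every treated patient once one has been replaced, and Section 5.3.2 gives a separate ground for leaving the same patients out.

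A reader might infer several stronger things that the documents do not support:

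- That replaced patients are failures by definition. The rule also covers withdrawal and intercurrent illness. The marrow window opens at about day 21, blood counts are weekly, and hematologic improvement counts as response, so a response before removal is possible.
- That AZA counts everyone treated at the dose, so the bias falls on LDAC alone. The AZA text does not say all and does not mention replaced patients. If Section 5.3.2 governs, it excludes the same patients in both arms, so a difference between arms is not established.
- That replacement will be used to refill phase II slots. The sentence is not restricted to phase I, but it sits among the DLT and MTD rules, and no text applies it to phase II response slots. A size for that effect would need an invented dropout rate.

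It is also fair to say that the shift is small beside an interval of 0.32 to 0.68, and that no formal success threshold depends on it.

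**Conclusion.** The concern holds as a gap in the definition of the efficacy denominator, affecting both arms. Sections 5.2.5.4, 12.3 and 5.3.2, followed as written, permit treated patients who leave before day 28 without a DLT to be left out of the primary response rate and of futility monitoring. Because most of them will probably lack a documented response, the response rate is biased upward and the futility rule is weakened.

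Under the assumption of 1 to 3 omitted patients, all non-responders, an LDAC result reported as 50.0% would be 1.9 to 5.2 points lower with everyone counted. Some futility decisions would change and others would not. If any omitted patient had responded, the effect would be smaller. The change should be made because the primary denominator must be settled before analysis and the repair is cheap.

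**What to change.** Three linked edits are needed; changing only the first two would leave Section 5.3.2 in conflict with them.

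1. In Section 5.2.5.4, state that replacement serves phase I DLT and MTD evaluation only.
2. In Section 12.3, for both arms, state that the response estimate and the futility rule include every patient who is eligible for that phase II cohort and received study treatment at the phase II dose. This includes phase I patients replaced for DLT evaluation. A patient with no documented response counts as a non-responder. The eligibility condition matters because phase I enrols regardless of FLT3 status (Section 4.1.2.2). The fixed figure of six should give way to this definition.
3. In Section 5.3.2, let the full-course definition support only a secondary per-protocol summary.

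The cost is a few sentences, with no change to treatment. The downside is that the reported response rate may be a few points lower.
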